10.2 Serious Adverse Event

A SAE is any experience that suggests a significant hazard, contraindication, side effect or precaution. With respect to human clinical experience, this includes any event which:

- results in death
- is life-threatening
- requires inpatient hospitalization or prolongation of hospitalization, unless

Statistical Analysis Plan

hospitalization is for:

- routine treatment or monitoring of the studied indication, not associated with any deterioration in condition.
- elective or pre-planned treatment for a pre-existing condition that is unrelated to the indication under study and has not worsened since the start of study drug
- treatment on an emergency outpatient basis for an event not fulfilling any of the definitions of a SAE given above and not resulting in hospital admission
- social reasons and respite care in the absence of any deterioration in the subject's general condition
- results in persistent or significant disability/incapacity or
- is a congenital anomaly/birth defect
- is a significant or important medical event that, based on appropriate medical judgment, may jeopardize the subject or may require intervention to prevent one of the other outcomes listed above.

A listing of all serious adverse events and serious adverse events report will be provided in Listing 16.2.7.3, and the summary of SAEs will be presented as Table 14.3.1.6.

10.3 Laboratory Evaluation

Clinical laboratory tests, including standard hematology, chemistry, and urinalysis:

Hematology

CBC, including Hb, Hct, RBC count, WBC count, WBC differential, platelet count and HgbA1c

Chemistry

ALT, AST, ALP, total bilirubin, BUN, Serum Cr, electrolytes (K, Na, Mg, Ca and P), blood glucose, lipid profile (LDL, HDL, triglycerides)

Urinalysis

pH, specific gravity, leukocyte, erythrocyte, protein

PSA Tumor Marker

PSA level

Testosterone Level

Testosterone level

Clinical laboratory data (hematology, biochemistry, and urinalysis) will be listed in Listings

Statistical Analysis Plan

16.2.8.2-16.2.8.4. Observations outside the normal range will be flagged. The abnormal values will be flagged with 'L' (low) for values below the lower limit of the laboratory's normal range or 'H' (high) for values above the upper limit of the laboratory's normal range. Clinically significant laboratory results will be marked as well. All original and repeated values will be listed.

The observed values of clinical laboratory data (hematology, biochemistry, and urinalysis) will be summarized for baseline, end of treatment, end of study, and change from baseline to end of treatment and end of study in Table 14.3.3.1~Table 14.3.3.3. Also, the clinical laboratory data transition status from baseline to end of treatment and end of study will be presented in Table 14.3.3.4~Table 14.3.3.6.

The PSA levels will be listed by subject in Listing 16.2.8.5; the testosterone level will be listed by subject in Listing 16.2.8.6.

Abnormal laboratory values of hematology, biochemistry and urinalysis will be listed in Listing 16.2.8.1.

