2. Blinding:  open-label  evaluator blind  single blind  double blind  double dummy  other
3. Randomized:  yes  no
4.  Parallel  Cross-over  Other Single-arm, open label
5. Duration of study: approx. 1 year (2 years total exposure)
6. Titration:  forced  optional  none
7.  Multi-national  Multi-center  Single center

VI. Endpoints

Primary endpoints:

1. Determine the safety and tolerability by:

- Clinically significant abnormal laboratory assessment (including liver function (AST, ALT, ALP), renal function (BUN, Serum Cr), complete blood count with platelets, clinical chemistries (K, Na, Mg, Ca and P), urinalysis, serum glucose, lipid profile (LDL, HDL, triglycerides) and HgbA1c)
- Adverse event (AE) reporting
- Clinically significant changes from baseline in 12-lead resting electrocardiograms (ECGs) per the Investigator's judgment

VII. Selection criteria:

1. Main inclusion criteria*:

- (1) Complete 12 months of treatment with LMIS 50 mg under Protocol FP01C-13-001. If a subject wishes to enter the Extension study after more than 28 days following his end of study visit for Protocol FP01C-13-001, his serum testosterone level should be repeated at the screening visit to confirm that his castrate-level testosterone has been maintained.
- (2) Laboratory values
 - Absolute neutrophil count \geq 1,500 cells/ μ L
 - Platelets \geq 100,000 cells/ μ L
 - Hemoglobin \geq 10 gm/dL
 - Total bilirubin \leq 1.5 \times upper limit of normal (ULN)
 - AST (SGOT) \leq 2.5 \times ULN
 - ALT (SGPT) \leq 2.5 \times ULN
 - Serum creatinine \leq 1.5 mg/dL
 - Lipid profile within acceptable range according to investigator's opinion
 - Serum glucose within acceptable range according to investigator's

opinion

- HgbA1c within acceptable range according to investigator's opinion
- Clinical chemistries (K, Na, Mg, Ca and P) within acceptable range according to investigator's judgment
- Urinalysis within normal range according to the investigator's judgment

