7.2.2. Hematological / Biochemistry Examinations

Fasting blood samples will be collected for hematological, biochemistry and biological examinations.

Hematological tests will include complete blood count (CBC), including hemoglobin (Hb), hematocrit (Hct), red blood cells (RBC), white blood cells (WBC), WBC differential (neutrophils, eosinophils, basophils, lymphocytes and monocytes) platelet counts and HgbA1c. Biochemistry tests will include ALT, AST, ALP, total bilirubin, BUN, Serum Cr, electrolytes (K, Na, Mg, Ca and P), blood glucose and lipid profile (LDL, HDL, triglycerides).

Laboratory tests, except for the HgbA1c, will be performed during the Screening Visit and at Day 84 ±7 days, Day 168±7 days, Day 252 ±7 days and Day 336±7 days. The HgbA1c will be performed at the final visit (Day 336 or End of Study Visit).

PSA will be performed at Day 84±7 days, Day 168±7 days (prior to dosing), Day 252±7 days, and at the final visit (Day 336±7 days or End of Study Visit).

The End of Study laboratory tests, HgbA1c and PSA assessments for Protocol FP01C-13-001 will be used as the Baseline assessment for this study.

Blood samples for laboratory tests will be collected in the hospital or at the investigative site and will be sent to the Central Laboratory for analyses.

*If the patient completed 12 months of treatment with LMIS 50 mg more than 28 days prior to entering the Extension study, the testosterone level should be repeated and the repeat test should indicate that the patient maintains a castrate-level of testosterone. In addition, the ECOG, PE, ECG, laboratory and PSA tests should be repeated.

If the patient has completed 12 months of treatment with LMIS 50 mg under Protocol FP01C-13-001 within the last 28 days, they will be allowed to enter the Extension study without repeating the testosterone measurements, ECG, PE, laboratory and the PSA tests.

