7.2.3. Urinalysis

A urine sample will be collected for urinalysis. The urinalyses will include urine pH, specific gravity, leukocyte, erythrocyte and protein.

The urinalysis will be performed at Screening, Day 84 ±7 days, Day 168±7 days (prior to dosing), Day 252 ±7 days and Day 336±7 days (or End of Study Visit).

The End of Study urinalysis for Protocol FP01C-13-001 will be used as the Baseline

assessment for this study.

Urine samples will be collected in the hospital or at the investigative site and will be sent to the Central Laboratory for analyses.

*If the patient completed 12 months of treatment with LMIS 50 mg more than 28 days prior to entering the Extension study, the testosterone level should be repeated and the repeat test should indicate that the patient maintains a castrate-level of testosterone. In addition, the ECOG, PE, ECG, laboratory and PSA tests should be repeated.

If the patient has completed 12 months of treatment with LMIS 50 mg under Protocol FP01C-13-001 within the last 28 days, they will be allowed to enter the Extension study without repeating the testosterone measurements, ECG, PE, laboratory and the PSA tests.

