3.5 Endpoints

Determine the safety and tolerability by:

- 1) Assessment of clinically significant abnormal lab data, including liver function (AST, ALT, ALP), renal function (BUN, Serum Cr), complete blood count with platelets, clinical chemistries (K, Na, Mg, Ca and P), urinalysis, serum glucose, lipid profile (LDL, HDL, triglycerides) and HgbA1c
- 2) Adverse event (AE) reporting
- 3) Clinically significant changes from baseline in 12-lead resting electrocardiograms (ECGs) per the Investigator's judgment

The safety endpoints include:

- Adverse event (AE)
- Laboratory data
- Vital signs
- Physical examination
- 12-lead resting electrocardiograms (ECGs)

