System Organ Class 1	Preferred Term 2	E	nn	(xx.x%)	E	nn	(xx.x%)	E	nn	(xx.x%)	
System Organ Class 2	Preferred Term 1	E	nn	(xx.x%)	E	nn	(xx.x%)	E	nn	(xx.x%)	
System Organ Class 2	Preferred Term 2	E	nn	(xx.x%)	E	nn	(xx.x%)	E	nn	(xx.x%)	
Death AE											
System Organ Class 1	Preferred Term 1	E	nn	(xx.x%)	E	nn	(xx.x%)	E	nn	(xx.x%)	
System Organ Class 1	Preferred Term 2	E	nn	(xx.x%)	E	nn	(xx.x%)	E	nn	(xx.x%)	
System Organ Class 2	Preferred Term 1	E	nn	(xx.x%)	E	nn	(xx.x%)	E	nn	(xx.x%)	
System Organ Class 2	Preferred Term 2	E	nn	(xx.x%)	E	nn	(xx.x%)	E	nn	(xx.x%)	

E is the number of events, n is the number of subjects, and the AE percentage: 100%*The number of subjects with event (n) / Total number of subjects in Safety population (N)
[Program: \\Foresee\\FP01C-13-001\\SAP\\Table\\S_AE.sas]

Table 14.3.2: Summary of Study Medication (Safety Population)

Variables / Status	Total (N=XX)
Received first administration	
Yes	nn (xx.x%)
No	nn (xx.x%)
Received second administration	
Yes	nn (xx.x%)
No	nn (xx.x%)
Treatment duration (days)	
n	nn
mean (SD)	xx.x (xx.x)
SE	xx.x
median (min, max)	xx.x (xx.x, xx.x)
Study duration (days)	
n	nn
mean (SD)	xx.x (xx.x)
SE	xx.x
median (min, max)	xx.x (xx.x, xx.x)

Treatment duration (days) is defined as (last administered date – first administered date + 1); and study duration (days) is defined as (last visit date – first administered date + 1).
 [Program: \\Foresee\\FP01C-13-001\\SAP\\Table\\S_EX.sas]

Table 14.3.3.1: Summary of Laboratory Assessments - Hematology (Safety Population)

Variables / Status	Total (N=XX)
Hematology at Screening (V1)	
n	nn
mean (SD)	xx.x (xx.x)
SE	nn (xx.x%)
median (min, max)	xx.x (xx.x, xx.x)
Normal	nn (xx.x%)
Abnormal - NCS	nn (xx.x%)
Abnormal - CS	nn (xx.x%)
Not Done	nn (xx.x%)
Hematology on Day 168 (V4)	
n	nn
mean (SD)	xx.x (xx.x)
SE	nn (xx.x%)
median (min, max)	xx.x (xx.x, xx.x)
Normal	nn (xx.x%)
Abnormal - NCS	nn (xx.x%)
Abnormal - CS	nn (xx.x%)
Not Done	nn (xx.x%)
Hematology on Day 336 (V6/EOS)	
n	nn
mean (SD)	xx.x (xx.x)
SE	nn (xx.x%)
median (min, max)	xx.x (xx.x, xx.x)
Normal	nn (xx.x%)
Abnormal - NCS	nn (xx.x%)
Abnormal - CS	nn (xx.x%)
Not Done	nn (xx.x%)
Hematology change on Day 168 (V4)	
n	nn

*Paired T test or Wilcoxon signed rank test will be used to test the change from baseline for continuous variables.
 [Program: \\Foresee\\FP01C-13-001\\SAP\\Table\\S_LB.sas]

Table 14.3.3.1: Summary of Laboratory Assessments - Hematology (Safety Population)

Variables / Status	Total (N=XX)

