Abnormal - NCS	nn (xx.x%)
Abnormal - CS	nn (xx.x%)
Not Done	nn (xx.x%)
Urinalysis change on Day 168 (V4)	
n	nn

*Paired T test or Wilcoxon signed rank test will be used to test the change from baseline for continuous variables.
 [Program: \\Foresee\\FP01C-13-001\\SAP\\Table\\S_LB.sas]

Table 14.3.3.3: Summary of Laboratory Assessments - Urinalysis (Safety Population)

Variables / Status	Total (N=XX)
mean (SD)	xx.x (xx.x)
SE	nn (xx.x%)
median (min, max)	xx.x (xx.x, xx.x)
P-value*	x.XXXX
Urinalysis change on Day 336 (V6/EOS)	
n	nn
mean (SD)	xx.x (xx.x)
SE	nn (xx.x%)
median (min, max)	xx.x (xx.x, xx.x)
P-value*	x.XXXX

*Paired T test or Wilcoxon signed rank test will be used to test the change from baseline for continuous variables.
 [Program: \\Foresee\\FP01C-13-001\\SAP\\Table\\S_LB.sas]

Table 14.3.3.4: Summary of Laboratory Assessments Transition Status - Hematology (Safety Population)

Variables / Status	Screening (V1)			
	Normal	Abnormal - NCS	Abnormal - CS	Not Done
Hematology on Day 168 (V4)				
Normal	nn (xx.x%)	nn (xx.x%)	nn (xx.x%)	nn (xx.x%)
Abnormal - NCS	nn (xx.x%)	nn (xx.x%)	nn (xx.x%)	nn (xx.x%)
Abnormal - CS	nn (xx.x%)	nn (xx.x%)	nn (xx.x%)	nn (xx.x%)
Not Done	nn (xx.x%)	nn (xx.x%)	nn (xx.x%)	nn (xx.x%)
Hematology on Day 336 (V6/EOS)				
Normal	nn (xx.x%)	nn (xx.x%)	nn (xx.x%)	nn (xx.x%)
Abnormal - NCS	nn (xx.x%)	nn (xx.x%)	nn (xx.x%)	nn (xx.x%)
Abnormal - CS	nn (xx.x%)	nn (xx.x%)	nn (xx.x%)	nn (xx.x%)
Not Done	nn (xx.x%)	nn (xx.x%)	nn (xx.x%)	nn (xx.x%)

Table 14.3.3.5: Summary of Laboratory Assessments Transition Status - Biochemistry (Safety Population)

Variables / Status	Screening (V1)			
	Normal	Abnormal - NCS	Abnormal - CS	Not Done
Biochemistry on Day 168 (V4)				
Normal	nn (xx.x%)	nn (xx.x%)	nn (xx.x%)	nn (xx.x%)
Abnormal - NCS	nn (xx.x%)	nn (xx.x%)	nn (xx.x%)	nn (xx.x%)
Abnormal - CS	nn (xx.x%)	nn (xx.x%)	nn (xx.x%)	nn (xx.x%)
Not Done	nn (xx.x%)	nn (xx.x%)	nn (xx.x%)	nn (xx.x%)
Biochemistry on Day 336 (V6/EOS)				
Normal	nn (xx.x%)	nn (xx.x%)	nn (xx.x%)	nn (xx.x%)
Abnormal - NCS	nn (xx.x%)	nn (xx.x%)	nn (xx.x%)	nn (xx.x%)
Abnormal - CS	nn (xx.x%)	nn (xx.x%)	nn (xx.x%)	nn (xx.x%)
Not Done	nn (xx.x%)	nn (xx.x%)	nn (xx.x%)	nn (xx.x%)

Table 14.3.3.6: Summary of Laboratory Assessments Transition Status - Urinalysis (Safety Population)

Variables / Status	Screening (V1)			
	Normal	Abnormal - NCS	Abnormal - CS	Not Done
Urinalysis on Day 168 (V4)				
Normal	nn (xx.x%)	nn (xx.x%)	nn (xx.x%)	nn (xx.x%)

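### No laboratory table counts, per parameter, the men with a clinically significant value at any time on study; the tables show three separate visits only

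*SAP*

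**What the plan says.** The Protocol Synopsis, item VI, puts "Clinically significant abnormal laboratory assessment" first among the primary endpoints. Protocol 2.2 and SAP 3.5 repeat it, with the parameters named. None of these places says how it is to be counted.

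Sampling is more frequent than tabulation. Protocol 7.2.2 states: "Laboratory tests, except for the HgbA1c, will be performed during the Screening Visit and at Day 84", and goes on to Days 168, 252 and 336. Protocol 7.2.3 gives urinalysis the same visits: "The urinalysis will be performed at Screening, Day 84", then the same three later days. HgbA1c has one scheduled post-baseline sample, at the final visit.

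For the tables, SAP 10.3 says: "The observed values of clinical laboratory data (hematology, biochemistry, and urinalysis) will be summarized for baseline, end of treatment, end of study". It adds that "the clinical laboratory data transition status from baseline to end of treatment and end of study will be presented". The shells place end of treatment at Day 168 (V4) and end of study at Day 336 (V6/EOS). At each tabulated visit they give counts of Normal, Abnormal - NCS, Abnormal - CS and Not Done. Abnormal values are also listed by subject and visit (Listing 16.2.8.1), all laboratory values appear in Listings 16.2.8.2 to 16.2.8.4 with CS results marked, and unscheduled assessments go to Listing 16.2.14.

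**The concern.** A safety reader's first question on this endpoint is how many men had a CS value for a given parameter during the extension. No laboratory table answers it. Two of the four scheduled post-baseline draws, and every unscheduled one, are outside the tables.

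The two omitted visits also differ in kind from the two that are kept. The Day 168 sample is taken before the second injection, and Day 336 is 168 days after its planned date, so on schedule both tabulated visits fall at the end of a dosing interval. Days 84 and 252 are the only scheduled mid-interval draws. An abnormality that appeared and resolved within an interval would be in no laboratory table.

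At stake is a direct summary of the first-listed endpoint in a study whose only purpose is safety over up to one more year of treatment.

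**Working it through.** **1. Schedule against tables** (Protocol Table 1, 7.2.2 and 7.2.3; SAP 10.3 and shells). The shells are generic by panel, and I read them as repeated for each parameter, which the SAP does not state.

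| Visit | Hematology, biochemistry, urinalysis scheduled | Tables 14.3.3.1-14.3.3.3 | Tables 14.3.3.4-14.3.3.6 |
|---|---|---|---|
| Day 84 | yes | no | no |
| Day 168 | yes | yes | against Screening |
| Day 252 | yes | no | no |
| Day 336/EOS | yes | yes | against Screening |
| Unscheduled | as needed | no | no |
| Any post-baseline, or worst value | not applicable | no row | no row |

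The schedule shares one column between early termination and end of study, so early-termination results enter the V6/EOS row. For HgbA1c that row is in effect the any-time count, apart from unscheduled tests.

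**2. What the two tabulated visits determine.** Take the men in one Screening category, m of them, with a CS at Day 168 and b CS at Day 336. The shift tables link each visit to Screening but not to each other, so the number of different men who were CS at either visit satisfies

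max(a, b) ≤ different men ≤ min(a + b, m).

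With a = b = 5 and m of at least 10, this gives max(5, 5) = 5 to 5 + 5 = 10.

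**3. When the shift tables do help.** With several Screening categories, the limits are summed over categories. If the 5 at Day 168 were all Normal at Screening and the 5 at Day 336 were all Abnormal - NCS, the lower limit is 5 + 5 = 10 and the upper limit is also 10, so the count is settled. The tables therefore sometimes settle the two-visit count, but not in general.

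**4. All four visits.** The lower limit stays at 5. The laboratory tables set no useful upper limit, because Days 84 and 252 are absent. If each of those visits also had 5 CS men (an assumption), the count could be anything from 5 to 4 × 5 = 20. On the SAP 4.3 ceiling of 137 men that is 5/137 = 3.6% to 20/137 = 14.6%.

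**5. Scale, by illustration only.** Assume a CS probability p at each of four visits. If the same men are CS every time, the any-time proportion is p. If visits are independent, it is 1 − (1 − p)^4.

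| Assumed p | Same men each visit | Independent visits |
|---|---|---|
| 1% | 1.0% | 3.9% |
| 3% | 3.0% | 11.5% |
| 5% | 5.0% | 18.5% |

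The documents give neither p nor the within-man correlation. The table shows that the gap could be nil or severalfold. It does not estimate the gap.

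**The case against.** The strongest reply has three parts.

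- **No commitment is broken.** The endpoint is worded as an assessment of CS data, not as an ever count. Protocol 10.3 plans laboratory summaries at Baseline and End of Study only, and the SAP already adds Day 168, the CS and NCS categories and shift tables. This stands.
- **An any-time count already exists in part.** Protocol 9.1 has abnormal laboratory values recorded as adverse events when the investigator judges them clinically significant. Table 14.3.1.2 counts subjects by preferred term whatever the visit, so Day 84, Day 252 and unscheduled results can reach it. This stands in part. Preferred terms are not laboratory parameters, and there is no laboratory subtotal. No reconciliation with the CS flags is planned. Under the SAP 10.1 definition of a new treatment-emergent event, a CS value that persists unchanged from before the first extension dose need not be counted as new.
- **The listings hold everything.** With at most 137 men, the count could be made by hand. This is true, and no data are lost. It is still an awkward way to obtain a basic number for the first-listed endpoint.

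A reader might go further and infer that the planned tables misstate the abnormality rate by some percentage, or that the endpoint goes unanalysed. The documents support neither. The rows are labelled by visit, nothing in the SAP adds visits together or presents one visit as cumulative incidence, and any percentage error would depend on assumed rates and correlations.

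**Conclusion.** The point holds as a recommended improvement to reporting. CS laboratory status is tabulated at Screening, Day 168 and Day 336/EOS only, and the number of men ever CS for a parameter cannot in general be obtained from the laboratory tables. The 5-to-10 example rests on one stated condition, that all the men share a Screening category of at least 10. Where Screening categories differ, the shift tables may narrow or settle the two-visit count.

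The actual size of the gap is not determined by the documents: it is nil if the same men are CS at every visit and grows as abnormalities become more transient. The missed-visit part does not apply to HgbA1c. This is neither an error in the plan nor a loss of data.

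**What to change.** For each parameter, add two items to the laboratory tables:

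- n (%) of subjects with any post-baseline Abnormal - CS result;
- a shift from baseline to the worst post-baseline category, ordered Normal, Abnormal - NCS, Abnormal - CS.

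Use all scheduled, early-termination and unscheduled results. The denominator is the subjects with at least one post-baseline result for that parameter. The shift separates men who were already CS at baseline from those who became so. Adding Day 84 and Day 252 rows alone would not be enough, since they would be two more unlinked cross-sections.

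State the baseline explicitly. Protocol 7.2.2 and 7.2.3 use the parent study's End of Study results, while the shells use Screening (V1), where men entering within 28 days need no repeat laboratory tests. Take the last result before the first extension dose: the parent study's End of Study value, or the repeat Screening value where one was taken.

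The cost is a few extra table rows from data and CS flags already collected. Reported abnormality rates may be somewhat higher than in the visit-by-visit rows.

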-------------	--------	---------------	----------------	--------------------------	-------------------	------------	-------------------------------	------------------------	---------	----------	------------	--------------	--------------	--------------------	---------

*Onset Day is defined as: Date of onset - Date of first administration + 1.

Listing 16.2.8.1: Laboratory Test Abnormality

Subject No.	Visit	Sampling Date (dd-mmm-yyyy)	Category	Item	Result	Units	Normal Range	Judgment	Flag*	If Any Protocol Deviation, Please Specify
-------------	-------	-----------------------------	----------	------	--------	-------	--------------	----------	-------	---

*Flag for Out-of-Range Values: 'L' (low)- below the lower limit of normal range; 'H' (high)- above the upper limit of normal range.

Listing 16.2.8.2: Laboratory Test - Hematology

Subject No.	Visit	Sampling Date or N/A (dd-mmm-yyyy)	Item	Result	Units	Normal Range	Judgment	Flag*	If Any Protocol Deviation, Please Specify
-------------	-------	------------------------------------	------	--------	-------	--------------	----------	-------	---

*Flag for Out-of-Range Values: 'L' (low)- below the lower limit of normal range; 'H' (high)- above the upper limit of normal range.

Listing 16.2.8.3: Laboratory Test - Biochemistry

Subject No.	Visit	Sampling Date or N/A (dd-mmm-yyyy)	Item	Result	Units	Normal Range	Judgment	Flag*	If Any Protocol Deviation, Please Specify
-------------	-------	------------------------------------	------	--------	-------	--------------	----------	-------	---

Listing 16.2.8.4: Laboratory Test - Urinalysis

Subject No.	Visit	Sampling Date or N/A (dd-mmm-yyyy)	Item	Result	Units	Normal Range	Judgment	Flag*	If Any Protocol Deviation, Please Specify
-------------	-------	------------------------------------	------	--------	-------	--------------	----------	-------	---

*Flag for Out-of-Range Values: 'L' (low)- below the lower limit of normal range; 'H' (high)- above the upper limit of normal range.

Listing 16.2.8.5: PSA Tumor Marker

Subject No.	Visit	Sampling Date (dd-mmm-yyyy)	N/A or Not Done	Result	If Any Protocol Deviation, Please Specify
-------------	-------	-----------------------------	-----------------	--------	---

Listing 16.2.8.6: Testosterone Level

Subject No.	Visit	Sampling Date (dd-mmm-yyyy)	N/A or Not Done	Result	If Any Protocol Deviation, Please Specify
-------------	-------	-----------------------------	-----------------	--------	---

Listing 16.2.9: Vital Signs

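### Laboratory status and transition tables merge low and high results within each significance level, so the direction of a shift is lost from the categorical summaries (minor)

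*SAP*

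**What the plan says.** SAP section 10.3 plans two kinds of laboratory summary table. The first, Tables 14.3.3.1 to 14.3.3.3, gives values at baseline, end of treatment and end of study, and "change from baseline to end of treatment and end of study in Table 14.3.3.1~Table 14.3.3.3". The shells show n, mean, SD, SE, median, minimum, maximum and a p-value for the change. They also give counts at each visit in four categories: Normal, Abnormal-NCS, Abnormal-CS and Not Done. The second kind is the transition matrix: "the clinical laboratory data transition status from baseline to end of treatment and end of study will be presented in Table 14.3.3.4~Table 14.3.3.6". Those three shells cross the same four categories at Screening with the same four at Day 168 and Day 336.

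Direction is handled separately. In its paragraph on the by-subject listings, section 10.3 says "Observations outside the normal range will be flagged". Listings 16.2.8.1 to 16.2.8.4 carry a flag column beside the investigator's judgement, explained by the footnote "Flag for Out-of-Range Values: 'L' (low)- below the lower limit of normal range; 'H' (high)- above the upper limit of normal range". No summary table shell uses the flag.

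Clinically significant abnormal laboratory data come first among the endpoints in SAP section 3.5, and the protocol synopsis (VI) lists them as primary.

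**The concern.** A count of men who moved from normal to abnormal is useful for safety only if the reader knows which way they moved. Low and high potassium, calcium or glucose are different findings with different explanations. The protocol's own warnings have a direction: section 5.5 names impaired glucose tolerance and anaemia. Section 8.1 also permits oral glucose-lowering drugs and calcium supplements, so shifts either way are plausible for glucose and calcium. A Normal-to-Abnormal count for glucose would not show whether the anticipated effect or its opposite had occurred.

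The same merging affects the diagonal of the transition matrix, which a reader takes to mean no change. A man who is low at Screening and high at Day 336, at the same significance level, is counted there with men whose result stayed where it was.

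**Working it through.** The plan states no figure on this point, so there is none to reproduce. The check maps every directional transition onto the planned categories.

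**Inputs**
- Planned states (shells 14.3.3.4 to 14.3.3.6): Normal, Abnormal-NCS, Abnormal-CS, Not Done.
- States available if the L/H flag is joined to the judgement (Listings 16.2.8.1 to 16.2.8.4): Normal, Low-NCS, High-NCS, Low-CS, High-CS, Not Done.
- Maximum number of subjects: 137 (SAP section 4.3).
- Assumption: each shell is repeated for each test, since a mean or SD over a whole panel would have no meaning.

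**Cells per test and visit**
- With direction: 6 × 6 = 36.
- As planned: 4 × 4 = 16.
- Abnormal-to-abnormal transitions: 4 × 4 = 16 with direction, shown in 2 × 2 = 4 cells.
- Normal to abnormal: 4 transitions with direction, shown in 2 cells. Each planned cell adds new lows to new highs.

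**Reversals**
- Low to high or high to low: 2 directions × 2 starting levels × 2 later levels = 8.
- Those with the same significance level at both visits: 2 × 2 = 4. These fall on the diagonal: Low-NCS to High-NCS, High-NCS to Low-NCS, Low-CS to High-CS and High-CS to Low-CS.
- The other 4 appear as a change in significance only.

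**Illustration (counts assumed, not forecast)**
- Suppose 6 new lows and 6 new highs at one significance level for one test, among 137 men.
- Each direction: 6/137 = 4.4%.
- As the table shows it: 12/137 = 8.8%.
- A displayed 12 fits every split from 0 lows and 12 highs to 12 lows and 0 highs. The share in either direction could lie anywhere from 0% to 8.8%.
- If the lows change by −x and the highs by +x, their contribution to the summed change is 6(−x) + 6(+x) = 0, so the mean change does not reveal the split.

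**Where direction can still be found**
- Listings 16.2.8.1 to 16.2.8.4: for every flagged value, subject by subject.
- Minimum and maximum of change in Tables 14.3.3.1 to 14.3.3.3: in part. They describe at most two men per row and carry no significance status.
- Adverse event tables: protocol section 9.1 records a laboratory abnormality as an adverse event if it needs therapeutic action or is judged clinically significant. SAP section 10.1 then tabulates it by preferred term and by CTCAE grade. Direction shows if the reported term names it. NCS results normally do not reach these tables, and the tables contain no baseline-to-visit shift.

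**The case against.** The strongest reply is that clinically significant results, which are what the endpoint names, already reach Tables 14.3.1.2 and 14.3.1.3 as adverse events, usually under a term that states the direction and with a grade. With one arm and at most 137 men, the remaining cases can be read from Listing 16.2.8.1, which gives result, normal range, judgement and flag together. Protocol section 10.3 asks for transition matrices for vital signs, physical examination and ECG. For laboratory data it asks only for descriptive statistics and a paired test, so the SAP already goes further than it must. Much of this stands, and it is why the point is minor.

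It does not remove the point. The SAP lists laboratory data as a safety endpoint separate from adverse events, and a reader should not have to rebuild directional counts by hand from a listing. The adverse event route also leaves out NCS results and shifts from baseline.

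A reader might infer three stronger things that the documents do not support:
- That there is only one abnormal category. There are two, and the merging happens within each.
- That a man who goes from significantly low to significantly high is reported as unchanged. That is true of the transition tables alone. Inclusion criterion 2 (protocol section 4.1) also makes it unlikely: it requires electrolytes and glucose to be acceptable to the investigator and sets floors for haemoglobin, platelets and neutrophils. The baseline Abnormal-CS column should be nearly empty for the tests that matter most here.
- That the first-listed endpoint cannot be interpreted. The listings, the extremes of change and the adverse event tables keep enough to interpret it, with more effort.

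**Conclusion.** The point holds as a minor one. For tests that can be abnormal in both directions (for example K, Na, Mg, Ca, P, glucose, white cells and platelets), the categorical laboratory tables cannot show direction. The practical loss is that new lows and new highs are added together. The reversal on the diagonal is real by construction but probably rare. The loss is greatest for NCS results and for shifts from baseline, which the adverse event tables do not cover. Where only one direction is of concern, as with ALT, AST or urine protein, little is lost. No planned estimate or test becomes invalid.

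This rests on reading the shells as final and as applied test by test. The size of the effect depends on how many men go out of range in each direction, which the documents do not give.

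**What to change.** For two-sided tests, present Tables 14.3.3.1 to 14.3.3.6 by analyte with the categories Low-CS, Low-NCS, Normal, High-NCS, High-CS and Not Done, built from the L/H flag and the CS/NCS judgement already recorded. Keep the present categories where only one direction is of concern, and list in SAP section 10.3 which tests fall in each group. Because flag and judgement are separate columns, add one sentence on how a result judged abnormal but carrying no flag is classified.

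The cost is shell edits and programming. No protocol change or new data are needed. The drawback is longer tables: up to 36 cells per test and visit for at most 137 men, many of them sparse or empty.
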